This proposed study is a pragmatic, randomized, open-label clinical trial of 24 weeks of XR-NTX vs. O-NTX using a COMBINE-adapted Medical Management primary care treatment model. 234 adults ≥ 18 yo with alcohol dependence will be recruited from the community into treatment at a major New York City primary care site (Bellevue Hospital Center's Adult Primary Care Clinic). The primary outcome which powers this study is a dichotomous good clinical outcome defined by abstinence or moderate drinking, and as measured by the Timeline Followback and analyzed using an intention-to-treat approach among all randomized participants. Secondary outcomes include the incremental cost effectiveness of the two arms, differences between arms by continuous measures of alcohol intake (drinks/day, % days abstinent, time to first heavy drinking day, biomarkers), and the exploratory analysis of factors possibly associated with effectiveness, including gender, pre-treatment abstinence, and mu opioid receptor (OPRM1) genotypes.

Study Schema

2.0 Study Timeline: This NIAAA notice of grant award was issued on July 18, 2013, award number: 1R01AA020836-01A1. We expect a 3-month start up phase during which we will complete the protocol approval process, hire study personnel, assemble study supplies and complete local SOPs. Recruitment of 234 enrolled and randomized participants will take place over 3 years, or approximately 6-7 persons randomized monthly, based on our pilot study. The final 6 months of Year 5 will be devoted to the tail end of study visits, data cleaning and analysis, study close out, preparation of initial manuscripts, and dissemination and national presentations of results.

Timeline	Year 1	Year 2	Year 3	Year 4	Year 5
Finalize protocol and study team					
Recruitment					
Treatment					
Follow-up					
Data clean and analysis					
Dissemination of results					
Total Study Visits	566	1130	1135	484	5

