3.8 Preliminary Studies and the Investigative Team: Alcohol and XR-NTX Research at NYUMC

The foundation for our proposal was a single-arm evaluation of XR-NTX in monthly primary care medical management of alcohol dependence, led by Drs. [name], [name], and [name] (Co-Is).

XR-NTX plus Medical Management in Primary Care: This recent pilot showed evidence of the feasibility, acceptability and likely effectiveness of a 3-month course of XR-NTX plus MM for treatment of alcohol dependence among 72 community-recruited adults using an open-label, single-arm, proof-of-concept design.² Rates of uptake, retention and adherence with monthly XR-NTX were robust within the same two clinical settings we now propose and among a study population which was 15% African American, 22% Latino, and 60% Medicaid/Medicare or uninsured. *Baseline drinking in this cohort (57%, % heavy drinking days) was similar to that of the COMBINE (63%) and Garbutt (64%) trials.* Most eligible, consented patients initiated (90%) and completed (62% of those initiating injections, 56% of N=72 patients) three months of treatment not involving monetary or other incentives, excepting a single \$20 payment at the last visit, and medications and medical care at no cost (**Table 1**). The 3-month adherence rate we observed was only slightly lower than in the relatively intensive Garbutt efficacy trial of XR-NTX (74%).²⁶ These rates of adherence and treatment retention were also similar to uptake and adherence rates expected in primary care patients initiating pharmacotherapy for common chronic conditions, such as hypertension or high cholesterol.^{67,68,69} Finally, reductions in self-reported drinking reductions, including significantly fewer heavy drinking days, were significant and sustained among persons retained in treatment (**Table 1**). Thus, in this single-arm observational pilot, treating alcohol dependence in primary care settings with XR-NTX and monthly physician medical management appeared a feasible and possibly effective model of alcohol treatment.

Table 1. XR-NTX + MM in Primary Care²	Baseline	Month 1	Month 2	Month 3
% retained in treatment (received monthly injection)	N=72	90%	68%	56%*
% heavy drinking days, last 30 days (median), if retained	57%	2%	3%	7%
*62% of participants initiating XR-NTX injections completed 3 of 3 injections				

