7.2 Screening and Randomization

At the baseline visit, informed consent will be obtained and eligibility confirmed by the research coordinator and study physician. A subsequent randomization/treatment visit will then be scheduled within a 2 week time period. Several factors may be associated with naltrexone treatment success/failure. We will stratify urn randomization by gender and recruitment status (in-clinic vs. community referrals). Stratifying further, however, yields increasingly smaller cells, given 117 per arm; AA ethnicity, medication preference (monthly injectable vs. daily oral), and lead-in (3-day) abstinence will be analyzed as a priori predictors of effectiveness. Randomization is the starting point of the study (day 1, week 1).

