7.7 Research-only Assessment Visits

As in any large clinical trial of usual care, some participants in both arms will not be present for all scheduled treatment visits. In an attempt to 'de-link' complete cost, utilization, and longitudinal drinking data collection from a naturalistic observation of these same usual care patterns, we will conduct 3 Research-only Assessment visits at week 13, 25 and 48. These visits will not hinge on a participant's treatment retention status, will be heavily incentivized to encourage participation (\$100 for time and travel), and will be conducted preferably in-person but alternatively by telephone if a participant is otherwise unwilling or unable to appear in clinic. These visits will be carefully scheduled apart from MM treatment visits, which are otherwise not incentivized beyond the provision of no-cost care and medication, so as to minimize the influence of extra assessments, attention, and the monetary research participation incentive on a participant's willingness to continue with MM. Participants will be paid \$20 for the initial screening visit after completion of all research assessments and \$20 after completing the randomization visit.

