The primary outcome measure of this study is a binary measure of success defined by abstinence or moderate drinking only, as measured by the TLFb, with drop-outs from MM and research-only assessments assumed to have resumed baseline rates of heavy drinking, and therefore defined as good clinical outcome failures. Our analytic approach will be an intention-to-treat comparison of all randomized participants (N=234). The analysis will utilize a logistic regression with an indicator variable for treatment and covariate terms for baseline potential prognostic indicators that are not stratified for at randomization, including AA ethnicity, lead-in abstinence, medication preferences, baseline drinking severity, in-trial specialty treatment involvement, clinical site, and OPRM1 genotype. If the coefficient of treatment is significant the null hypothesis of equal treatment effect is rejected. Odds ratios will be calculated to quantify the risk to treatment failure of significant predictors (Secondary Aim 2: Patient-Level Predictors of Effectiveness: To identify patient-level characteristics associated with effectiveness in both arms). To differentiate time to a good clinical outcome failure, we will use a "cure model." The form of a cure model is $H(t) = 1 - p + pS(t)$; where $H(t)$ is the probability of failure at a time greater than t , p represents the probability of failure, and $S(t)$ the distribution of time to failure, conditional on failure occurring. The parameters will be estimated based both on Kaplan Meier methods and parametrically. The equality of the values of p for the two treatment arms will be tested using a nonparametric likelihood ratio test. For the parametric test, a logistic will be used to model p and a Weibull survival distribution will be used to model time to failure, $S(t)$. Both allow the use of covariates, which will complement the above logistic regression approach.

As originally proposed, naltrexone appears most effective at reducing heavy drinking, as opposed to producing complete abstinence, and all traditional alcohol treatment trial clinical endpoints, including continuous drinking and heavy drinking variables, as well as the CDT biomarker, which is specific for heavy drinking, are of great interest, and will be reported in the primary publication from this trial. In addition, rates

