of medication treatment adherence, and an alternative good clinical outcome, treatment retention AND no heavy drinking, will be reported. Treatment differences in % days abstinent, overall % heavy drinking days, time to first drink, and time to first heavy drinking day, will be compared using mixed model repeated measures (MMRM) analysis including terms for subject, treatment, and time by treatment interaction, and covariate terms for baseline variables. To examine differential treatment effects at each week, we will perform tests of simple main effects. The MMRM will assume a means model, an unstructured covariance matrix and estimation will be based on restricted maximum likelihood. The baseline values will be adjusted by the overall mean. The assumptions relating to the mixed-effects model will be reviewed by examining residual scatter plots to examine deviations from normality and to assess lack-of-fit. In case of violation of assumptions, a randomization test will be performed based on the same MMRM.

10.2 Hypothesis 2: XR-NTX treatment will be more cost effective than O-NTX. (Secondary Aim 1: Cost Effectiveness. To estimate the incremental cost effectiveness of XR-NTX vs. O-NTX both in conjunction with primary care-based medical management of alcohol dependence).

We will estimate the incremental cost-effectiveness of XR-NTX compared to O-NTX. In technical terms the incremental cost-effectiveness is the ratio of incremental costs to incremental benefits; in lay terms, the incremental cost-effectiveness indicates the 'bang for the buck' of XR-NTX compared to O-NTX. The incremental cost-effectiveness of XR-NTX treatment compared to O-NTX treatment is equal to (Cost of XR-NTX minus Cost of O-NTX) divided by (Effectiveness of XR-NTX minus Effectiveness of O-NTX).

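### Time to first drink and time to first heavy drinking day are assigned to a repeated-measures model that a single, possibly censored, value per person cannot support

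*Combined protocol and SAP*

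**What the plan says.** Section 10.1 lists four drinking outcomes and gives them one method. Two are percentages (days abstinent, heavy drinking days). For the other two, "time to first drink, and time to first heavy drinking day, will be compared using mixed model repeated measures (MMRM) analysis". The model has terms for subject, treatment, time by treatment and baseline covariates, with treatment comparisons at each week. "The MMRM will assume a means model, an unstructured covariance matrix and estimation will be based on restricted maximum likelihood". If its assumptions fail, "a randomization test will be performed based on the same MMRM".

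The study summary under Section 1.0 names one of the two as a secondary outcome, in a list of continuous intake measures: "days abstinent, time to first heavy drinking day, biomarkers". Time to first drink appears only in Section 10.1.

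Two other statements in Section 10.1 come close but do not apply. The cure model (Kaplan-Meier and Weibull) is for time to failure of the good clinical outcome. The rule for drop-outs, "with drop-outs from MM and research-only assessments assumed to have resumed baseline rates of heavy drinking", classifies the binary primary outcome and sets no event or censoring date.

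**The concern.** An MMRM needs several values per person. Time to first drink and time to first heavy drinking day give one value each, and that value is right-censored for anyone without an event by week 24 or whose TLFB record stops earlier. The specified analysis therefore cannot be delivered, and the fallback has the same defect.

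The analyst will have to choose a method after seeing open-label data, for outcomes that Section 10.1 commits to the primary publication. The two simplest workarounds are to treat observed time as the outcome, or to analyse only participants with events. Both are biased if TLFB observation differs by arm. The events-only version also loses power when observation is equal. Section 9.0 expects 40–50% of XR-NTX participants and under 20% of O-NTX participants to complete treatment, so unequal observation has to be considered.

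**Working it through.** **The plan's own figures.** The plan gives no figure for these two outcomes. Its power figures concern the binary primary outcome (20% vs 40%, Fisher's exact test). With two-sided alpha 0.05 (assumed; the plan does not state it) they reproduce: 0.844 at 100 per arm (stated 0.84) and 0.901 at 117 per arm (stated 0.90). Nothing below changes them.

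**Can the model be estimated?** N = 234, one value per person.

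- A weekly unstructured matrix over 24 weeks has 24 × 25 / 2 = 300 covariance parameters. One value per person gives 234 values and no within-person pairs.
- With a random subject term plus residual, the REML log-likelihood depends only on the sum of the two variances. On simulated data it was −959.323 whether the subject share was 0%, 25%, 50%, 75% or 99%.
- With fixed subject terms plus treatment, the design has 235 columns, 234 rows and rank 234, so treatment is aliased with subject.
- Time-by-treatment and weekly contrasts have no data.

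**Why observed time misleads.** For event hazard λ and loss hazard γ (both constant, independent), mean observed time to week 24 is [1 − exp(−24(λ + γ))] / (λ + γ). Take a median event time of 8 weeks in both arms, so λ = ln 2 / 8 = 0.0866 per week. If 80% and 60% remain observed at week 24, γ = −ln(0.8)/24 = 0.0093 and −ln(0.6)/24 = 0.0213. The means are 9.38 and 8.57 weeks: a difference of 0.81 weeks with no treatment effect.

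**Type I error by simulation.** Assumptions: 117 per arm, equal hazards, exponential event and loss times, cut-off at week 24, nominal 5% test, 4,000 replicates per cell (Monte Carlo SE about 0.35 points at 5%). The table gives rejection rates when observed time is the outcome.

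| TLFB observation to week 24 | median 2 wk | 4 wk | 8 wk | 16 wk |
|---|---|---|---|---|
| 80% vs 80% | 5% | 5% | 5% | 5% |
| 80% vs 70% | 5% | 5% | 8% | 9% |
| 80% vs 60% | 6% | 7% | 14% | 25% |
| 45% vs 20% (worst case) | 10% | 21% | 46% | 71% |

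Events-only rejects 5–6%, 6–7% and 9–19% across the three unequal rows. Log-rank rejects 4.5–5.8% throughout. The 45/20 row sets TLFB observation equal to expected treatment completion.

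**Power**, hazard ratio 0.6, 80% observed in both arms, 2,000 replicates per cell:

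| Method | median 2 wk | 4 wk | 8 wk | 16 wk |
|---|---|---|---|---|
| Events only | 0.95 | 0.75 | 0.30 | 0.09 |
| Observed time | 0.96 | 0.94 | 0.87 | 0.62 |
| Log-rank | 0.97 | 0.96 | 0.93 | 0.80 |

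Further runs of the simulation agreed within Monte Carlo error.

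**Which columns are closest?** Pilot Table 1 in Section 3.8 reports "heavy drinking days, last 30 days (median), if retained" as 2% at month 1, or 0.02 × 30 = 0.6 days. That suggests roughly half had a heavy day in the first month, so the 2- and 4-week columns are nearest for heavy drinking.

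**The case against.** Software can return a result for one record per person: the time terms drop out, the covariance shrinks to one variance, and a linear comparison remains. That is true, but it is not the model described, and it ignores censoring.

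Survival methods are already in Section 10.1 through the cure model, so extending them is an obvious repair. That also is true, but the text limits the cure model to another endpoint. The two workarounds simulated are not in the documents; they illustrate what might be done in the absence of a plan.

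The strongest objection is to size. Section 7.7 separates assessment from treatment: "These visits will not hinge on a participant's treatment retention status", and they are paid and can be done by telephone. TLFB is a calendar instrument, so a week-13 visit can recover earlier weeks. If every lost participant has TLFB through week 13, then even at 45/20 the observed-time method rejects at only about 4–6% for medians of 2 to 4 weeks, and about 10–11% at 8 weeks. This stands: the larger figures depend on early, constant-rate loss. The pilot anchor is also thin. It is a median among retained participants in a single XR-NTX arm and says nothing direct about O-NTX, drop-outs or time to first drink.

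The events-only power loss stands too: it needs no difference in observation between arms.

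**Conclusion.** The concern holds. The method named for these two outcomes is wrong as written, not merely short of detail, and nothing elsewhere in the plan replaces it. This conclusion does not depend on the simulations.

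The practical size is uncertain. With medians of 2 to 4 weeks and moderately unequal observation, type I error from using observed time is 5–7%; 10–21% is a worst case. Power loss from events-only analysis ranges from negligible at a 2-week median to severe at 8 weeks or more. These figures rest on assumed observation rates, exponential times and independent censoring.

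One named secondary outcome and one further reported outcome are affected. The primary analysis and sample size are not. It should be fixed before the data are analysed.

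**What to change.** - Delete the two outcomes from the MMRM sentence in Section 10.1. Keep MMRM for % days abstinent and % heavy drinking days, computed per interval.
- Define time from randomization (day 1, Section 7.2), counting qualifying drinking on day 1 as an event on day 1. Censor at the last TLFB-covered day or the end of week 24, whichever is earlier.
- Report Kaplan-Meier curves and a log-rank test stratified by gender and recruitment status, the Section 7.2 strata. Add a Cox model with covariates fixed in advance and measured before randomization, which excludes in-trial specialty treatment involvement. Explicitly extending the cure model would be a reasonable alternative.
- Because the plan assumes that drop-outs resume heavy drinking, censoring may be informative. Add a sensitivity analysis counting loss of TLFB data as an event. Report it as a bound, not the main test: with unequal but independent loss it rejects at 5–10% for 80/70 and 10–74% for 45/20.

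The cost is SAP wording only; the TLFB already supplies daily dates.

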8.0 Assessments and Outcome Measures (Table 2)

Table 2. Visit Frequency (weeks)	0	1 ⁺	3	5 ⁺	7	9 ⁺	13 ⁺	17 ⁺	21 ⁺	25	26	48
XR-NTX vs. O-NTX + MM visits	x [#]	x [#]	x	x	x	x	x	x	x	x	x*	
Research-only assessment visits							x [#]			x [#]		x [#]

- *Safety documentation research visit
- # Compensation provided
- + Medication Dispensed

A comprehensive panel of measures is planned including standard measures of drug and alcohol use, medical status, and on-going treatment services utilization. The Timeline Follow Back (TLFB), Alcohol Use Disorders Identification Test (AUDIT), and Obsessive-Compulsive Drinking Scale (OCDS) are all validated measures used to identify alcohol and drug use along with regular urine toxicology and breathalyzer tests. The ASSIST will be used to assess for substance abuse or dependence and PHQ-9 for psychosocial diagnoses. The Seek, Test, Treat and Retain (STTR) assessment will collect various demographic information for each participant. The Economic Form 90, Cost Survey, and World Health Organization Quality of Life Survey (WHOQOL) will be used to assess treatment and criminal history as well as to ascertain economic data for cost-effectiveness outcome measures. The Morisky Medication Adherence Scale (MMAS-8) will be administered to the O-NTX arm only, providing information on adherence to self-administered medications. Fagerström's test for nicotine dependence and recall of cigarettes per day will be used to assess smoking cessation measures. Adaptations of the Stages of Change Questionnaire (SOC) and Responses to Stress Questionnaire (RTS) will look towards patient motivation, self-efficacy, and coping skills. The DSM-V criteria for PTSD, Generalized Anxiety Disorder 7-Item Scale (GAD-7), and Perceived Stress Scale (PSS) will be used to assess PTSD. Throughout the treatment phase, all adverse events (AEs) will be recorded on an AE form at all treatment visits.

Screening Visit (week 0): Informed Consent Form, Consent Quiz, medication preference question, DSM-V diagnostic interview and checklist, demographics, ASSIST, PHQ-9, WHOQOL, Alcohol Use Disorders Identification Test (AUDIT), Obsessive-Compulsive Drinking Scale, Fagerström, SOC, RTS, Questionnaire, DSM-V checklist for PTSD, GAD-7, PSS, history and physical exam, vital signs, liver function (AST, ALT, GGT), urine toxicology, pregnancy test, blood alcohol breathalyzer.

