Randomization Visit (week 1): Medical Management initial visit progress note, baseline biomarkers (CDT, Asp40 OPRM1 genotyping), urine toxicology, and Economic Form 90.

Treatment Visits (week 3-25): Timeline Followback (TLFB), recall of cigarettes per day, Morisky Medication Adherence Scale (MMAS-8, O-NTX arm only), Medical Management follow-up visit progress note, Adverse Event form, labs (weeks 13 and 25 only, AST, ALT, GGT, CDT).

Research-only Assessments* (week 13, 25, 48): TLFB, Economic Form 90, AUDIT, OCDS, WHOQOL, Fagerström**, SOC**, RTS**, DSM-V checklist for PTSD**, GAD-7**, and PSS**.

**Only at weeks 13 and 25.

Banked Genetic and Biomarker Testing: At randomization, participants will provide two separate blood draws (3 teaspoons blood for each) for genotyping and biomarker testing. Each of these blood samples will be labeled with the subject ID number and the date of blood draw only. No identifiable or private health information will be included on the labs prior to and when sent out for testing. Blood samples for a single biomarker (CDT) for heavy alcohol use will be drawn at randomization, weeks 13, and 25, and kept frozen at secure NYUMC facility freezer. At the conclusion of enrollment for study, samples will be sent in large batches to the Medical University of South Carolina (MUSC) and [name], a consultant on this protocol, laboratory. Results filed under the study ID only will be communicated and entered into the study database. Whole blood samples for a single nucleotide polymorphism (SNP) at the mu opioid receptor, the A118G OPRM1 SNP, will likewise be frozen, banked, and shipped in batch fashion for analysis at MUSC by

[name]. All samples will be destroyed following analysis and not preserved for future use. Results from either CDT or OPRM1 will be for research purposes only, will not be considered in real-time or used for participant counseling, and will be analyzed at conclusion of the study as secondary biomarkers and genetic baseline predictors of treatment outcomes.

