8.2 Secondary Drinking, Adverse Events, and Measures: drinking measures will be evaluated at each monthly visit (TLFB), along with self-reported O-NTX adherence (MMAS-8) and adverse events. Liver function tests (aspartate transaminase (AST), alanine transaminase (ALT), gamma-glutamyl transferase (GGT) and carbohydrate-deficient transferrin (CDT) will be measured every three months (week 0/1, 13, and 25), with AST, ALT, and GGT results available in real-time to study physicians. CDT, a validated biomarker for heavy drinking,^{82,83,84} is not in use or available at either facility, and will not be reported to participants or study physicians, but rather used as a secondary marker of baseline and in-treatment heavy drinking. CDT represents a 'cutting edge' alcohol biomarker, and one not previously studied in the context of an XR-NTX treatment trial. Analysis and interpretation of CDT results will be coordinated with [name] and his laboratory. Likewise, baseline assessments of drinking severity and psychiatric function (OCDS,⁸⁵ MINI-SCID,⁸⁶ Form 90⁸⁷) and naltrexone mu receptor susceptibility (Asp40 OPRM1 genotyping) will be captured for research purposes only, and not integrated into the clinician's MM strategies.

8.3 Cost Effectiveness Outcomes: Economic data will be derived primarily from the Economic Form 90,⁸⁸ Non-Study Medical Service and HHC electronic medical records assessments, EQ-5D (functional status),⁸⁹ and a cost survey or standardized question querying patient reports of specific non-medical related costs (including lost/gained work, lost/gained dependent care, transportation costs, arrests, motor vehicle accidents) collected at baseline and at week 13, 25, and 48 assessments. The week 48 assessment is included to gain longitudinal, post-treatment cost, drinking, and functional data at a small cost to the overall study budget. Whenever possible, verification of productivity (paystubs) and medical costs (medical records) will be sought to corroborate self-report.

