Cost-effectiveness analysis requires estimates of costs and estimates of effectiveness. Consequently, we will use primary data analyses from this study (Specific Aim 1 in the proposal) to inform costs and effectiveness estimates in the short-term, and we will synthesize these short-term estimates with published reports that allow us to estimate the longer-term, downstream costs and effects of the changes in alcohol consumption observed in Specific Aim 1. We will alternatively use societal and payer perspectives for assessing costs, and we will use the standard discount rate of 3% for costs and benefits.⁹⁰ The discount rate reflects the time preference with regard to costs and benefits (i.e., a dollar today is worth more to most people than an inflation-adjusted dollar at some time in the future). All costs will be inflated to 2011 US \$ using alternatively the consumer price index (CPI) for all goods and services and the CPI for Medical services (reflecting the ongoing debate over whether the Medical services CPI overestimates inflation because of the difficulty of discriminating the effect of service improvement from service inflation).

Short-term estimates of costs and effectiveness of XR-NTX compared with O-NTX. Short-term estimates of costs and effectiveness will be obtained from primary analysis of data from the trial proposed in Aim 1, using a combination of pre-specified medical record and survey endpoints. Cost assessment will be conceptually similar to recently published analyses of the COMBINE interventions,^{36,37,38} and will include medical and non-medical costs as well as payer and societal costs. Effectiveness assessment will include alcohol consumption measures as described elsewhere in this proposal, as well as quality of life. Quality of life will be assessed using the EQ-5D. The EQ-5D is among the most commonly used quality-of-life measure for informing cost-effectiveness analyses because it has minimal respondent burden, is well validated, and it yields utilities (preference-based measures on a scale of 0 to 1), the desired input for cost-effectiveness models. Because costs are skewed, incremental costs will be assessed using ordinary least squares (OLS) and median regression models with covariates for treatment intervention and other relevant factors, and conditional models may be used because of cost data that may include "zeros."

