Longer-term estimates of costs and effectiveness. To estimate the comparative effectiveness of XR-NTX relative to O-NTX over longer time horizons than are reflected by our data, we will incorporate these short-term results within a state-transition (Markov) computer simulation of outcomes that enables a cohort of hypothetical alcohol-dependent patients to be followed over time until death, and to be exposed to alternative alcohol interventions for specified time durations beyond the week 24 assessment. We will develop this simulation expressly for this proposal, drawing on our experience creating, validating, and using other computer simulations assessing the impact of alcohol interventions on long-term costs and benefits.^{91,92,93,94,95} The simulation will be able to aggregate the lifetime benefit of remitting alcohol dependence for designated periods of time using trial endpoints (e.g. frequency of heavy drinking days), and also can quantify benefits of the levels of improvement short of full remission (e.g. if alcohol

dependence remits but the patient still is an at-risk drinker). The simulation will estimate lifetime costs and benefits over a lifetime horizon, measured in both life-years and quality-adjusted life-years. (Quality-adjusted life years is a preference-based, quality of life metric that considers quality of life simultaneously with quantity of life, and instantiates the notion that a typical person would trade away some quantity of life to get a greater quality of life.) In sensitivity analyses we will consider time horizons shorter than lifetime (10 year and 20 year) because these horizons are sometimes preferred by decision makers, even though the longer, lifetime horizon is advocated by the Panel on Cost-Effectiveness in Health and Medicine.⁷⁷

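### The EQ-5D and cost survey that Section 8.3 plans are on none of the Section 8.0 visit lists, which schedule WHOQOL instead, so the trial-based utilities promised in Section 10.2 may not be collected

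*Combined protocol and SAP*

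**What the plan says.** Section 10.2 (short-term estimates) takes costs and effectiveness from trial data and counts quality of life as part of effectiveness: "Quality of life will be assessed using the EQ-5D". Its reasons include that "it yields utilities (preference-based measures on a scale of 0 to 1), the desired input for cost-effectiveness models". The trial results then enter a Markov simulation whose benefits are "measured in both life-years and quality-adjusted life-years".

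Section 8.3 lists the sources of economic data. Besides Economic Form 90 it names "Non-Study Medical Service and HHC electronic medical records assessments, EQ-5D (functional status") "and a cost survey or standardized question querying patient reports of specific non-medical related costs". The timing is "collected at baseline and at week 13, 25, and 48 assessments".

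The Section 8.0 overview gives a different set: "The Economic Form 90, Cost Survey, and World Health Organization Quality of Life Survey (WHOQOL) will be used to assess treatment and criminal history", and also to supply economic data for the cost-effectiveness measures. The visit lists follow. WHOQOL is on the screening list (week 0), Economic Form 90 is on the randomization list (week 1), and the Research-only list for weeks 13, 25 and 48 begins "TLFB, Economic Form 90, AUDIT, OCDS, WHOQOL". The EQ-5D and the cost survey are on none of them.

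**The concern.** Two parts of one protocol name different quality-of-life instruments for the same secondary aim. The analysis sections rely on the EQ-5D. The operational section schedules WHOQOL, for which the plan claims no utility property and gives no scoring route to one.

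Section 11.0 says coordinators enter data in real time on web-based case report forms. If those forms were built from the visit lists, there would be no EQ-5D form. A participant's health state at baseline or week 13 cannot be reliably reconstructed at the end of the trial. Secondary Aim 1, which has its own hypothesis, would then lack the trial-based utilities it was designed around. The patient-reported non-medical costs that Section 8.3 assigns to the cost survey (work, dependent care, transport, arrests, motor vehicle accidents) would be at risk wherever no other form asks for them.

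**Working it through.** The plan gives no figure to reproduce. The check is a comparison of every place where the four instruments are named.

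| Instrument | 8.0 overview | 8.0 visit lists | 8.3 | 10.2 |
|---|---|---|---|---|
| EQ-5D | not named | none | named | named, as source of utilities |
| WHOQOL | named | weeks 0, 13, 25, 48 | not named | not named |
| Cost survey | named | none | named (or a standardized question) | not named; survey endpoints and non-medical costs are mentioned |
| Economic Form 90 | named | weeks 1, 13, 25, 48 | named | not named |

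1. **Timing in 8.3.** The timing phrase closes a list, so it could grammatically attach to the cost survey alone. Two things support reading it across the list. Economic Form 90 does appear on the visit lists at baseline (week 1) and weeks 13, 25 and 48. The next sentence of 8.3 says week 48 is there partly for functional data, and 8.3 labels the EQ-5D as functional status.

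2. **EQ-5D.** Sections 8.3 and 10.2 require it. The 8.0 overview and all visit lists omit it, including the treatment-visit list for weeks 3 to 25. WHOQOL shows the reverse pattern. This is a conflict over the instrument as well as a gap in a list.

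3. **Cost survey.** The 8.0 overview and 8.3 agree that it is used, and no rival instrument is named. Here the fault is only that no visit list carries it.

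4. **What remains if the lists alone are followed.** Economic Form 90 is still collected. The 8.0 overview groups it with the instruments covering treatment history, criminal history and economic data. The protocol does not itemize it, so its overlap with the cost survey is unknown. Section 8.3 also seeks medical records and pay records where possible. Section 10.2 takes the simulation's inputs on how alcohol affects quality of life, medical costs and non-medical consequences from published reports, and mentions collisions and arrests.

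5. **What does not remain.** Participant-level EQ-5D utilities, and cost-survey items that Economic Form 90 does not ask for.

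6. **Count of forms.** 234 participants × 4 time points = 936 planned EQ-5D forms. This is the most that could be missing if 8.3 were disregarded at every visit; it does not predict the loss.

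**The case against.** The strongest reply is that the visit lists are plainly not exhaustive, so an omission proves little. Section 8.1 requires the Timeline Followback at every Medical Management and Research-only visit, and Table 2 marks weeks 0 and 1 as Medical Management visits, yet neither of those lists includes it. The MINI-SCID in 8.2 and the Non-Study Medical Service assessment in 8.3 are on no list either. No passage says that WHOQOL replaces the EQ-5D, and the two could coexist. Staff who read 8.3 would collect both the EQ-5D and the cost survey.

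This stands as far as it goes: the documents do not show that the EQ-5D was dropped. It does not remove the conflict. The 8.0 overview, which is not a visit list, gives WHOQOL the economic role and leaves out the EQ-5D. The lists are detailed enough to be used operationally; they include the consent quiz and the breathalyzer, and a footnote limits some forms to weeks 13 and 25. They also carry the smoking and PTSD measures that Section 3.7 describes for active and newly enrolled patients. That suggests Section 8.0 was revised after recruitment began without the EQ-5D being added.

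A reader might also infer that the assessment section omits both instruments altogether, that no QALYs could be produced, or that the societal perspective would have no non-medical costs. The documents support none of these. Section 8.3 is part of the assessment section and names both instruments, and 8.0 names the cost survey. Simulated QALYs can draw on trial drinking endpoints and published reports. Economic Form 90 remains scheduled. The $100,000 per QALY figure in 10.2 is an example within the simulation exercise for a negative trial, and is not described as resting on trial utilities.

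**Conclusion.** The inconsistency is real and should be corrected. Sections 8.3 and 10.2 depend on the EQ-5D, the 8.0 overview puts WHOQOL in the economic role, and the visit lists carry neither the EQ-5D nor the cost survey. The consequence is conditional on data collection following the visit lists, and the documents do not say whether it did. Under that condition all participant-level utilities are lost, and an unknown share of the cost-survey items with them. Literature-based QALYs and non-medical costs survive, but they are not the trial-based short-term estimates that 10.2 promises.

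No effect on the cost-effectiveness ratio can be calculated. The conclusion rests on reading the timing in 8.3 as covering the EQ-5D, and on the absence of any stated route from WHOQOL to utilities. It affects one secondary aim and leaves the primary analysis untouched.

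**What to change.** In Section 8.0, add the EQ-5D and the cost survey to the baseline list (week 0 or 1) and to the Research-only list for weeks 13, 25 and 48. In the 8.0 overview, name the EQ-5D as the source of utilities and describe WHOQOL as a descriptive measure.

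Check which forms have actually been used. If the EQ-5D has not been collected, state before analysis how utilities will be obtained, whether from WHOQOL by a named method or from published values, and restate 10.2 so that it no longer promises EQ-5D utilities from the trial. If the cost survey has not been collected, state which non-medical costs Economic Form 90 covers and which will come from published reports.

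The cost is protocol wording plus one short form and a cost survey at visits that already take place. Both are already planned in 8.3, and 10.2 itself describes the EQ-5D as light on respondents.
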